6.12.1.3. Severity

The severity of the AE should be characterized as "mild, moderate or severe" according to the following definitions:

- Mild events are usually transient and do not interfere with the subject's daily activities.
- Moderate events introduce a low level of inconvenience or concern to the subject and may interfere with daily activities.
- Severe events interrupt the subject's usual daily activity

6.12.1.4. Drug-Event Relationship

The causal relationship between the study drug and the AE should be characterized according to the following:

- Unrelated – there is not a reasonable possibility that the study drug caused the AE.

Confidential Page 60 of 94

- Unlikely suggests that only a remote connection exists between the study drug and the event. Other conditions, including concurrent illness, progression or expression of the disease state or reaction to concomitant medication, appear to explain the AE.
- Possible suggests that the association of the AE with the study drug is unknown, however the event is not reasonably supported by other conditions.
- Probable suggests that a reasonable temporal sequence of the AE with drug administration exists and, in the Investigator's clinical judgment, it is likely that a causal relationship exists between the drug administration and the AE, and other conditions (concurrent illness, progression or expression of the disease state, or concomitant medication reactions) do not appear to explain the AE.
- Certain clear evidence to suggest a causal relationship, and other possible contributing factors can be ruled out. The clinical event, including an abnormal laboratory test result, occurs in a plausible time relationship to drug administration and cannot be explained by concurrent disease or other drugs or chemicals.

The relationship with COVID-19 will also be registered (in case it is ongoing at the moment of the study treatment phase).

6.12.1.5. **Outcome**

The outcome of the adverse event should be classified according to the following definitions:

- Recovered / resolved: the event has resolved (no further symptoms are present and no treatment is being received by the subject).
- Recovered / resolved with sequelae: the event has resolved but there may be lingering effects present (e.g., a scar following a cut or abrasion).
- Fatal: the subject died as a result of the event. This code should only be used for the
 event that caused the death, not any event that was present at the time of the subject's
 death. Fatal events require immediately reporting to the Sponsor (or an authorized
 representative).
- Unknown: may only be used in the event that the subject is lost to follow-up and no reliable data can be obtained.

All efforts should be made to classify the AE according to the above categories.

Note: when the AE is ongoing, the outcome will remain blank on the Adverse Events form in the eCRF

6.12.1.6. Follow-up of Adverse Events

All AEs occurring during the study are to be followed up in accordance with good medical practice until resolved or judged no longer clinically significant, or if a chronic condition, until fully characterized. All follow-up results are to be reported to the Sponsor (or an authorized representative).

6.12.1.7. Serious Adverse Events (SAEs)

Definitions of Serious Adverse Event (SAE)

Any untoward medical occurrence that at any dose:

Results in death,

Confidential Page 61 of 94

- Is life-threatening (an event in which the subject was at risk of death at the time of the
 event; it does not refer to an event which hypothetically might have caused death if it
 were more severe),
- Requires inpatient hospitalization or prolongation of an existing hospitalization,
- Results in persistent or significant disability/incapacity,
- Is a congenital anomaly/birth defect,
- Is any suspected transmission via a medicinal product of an infectious agent,
- Is considered an important medical event (an event that may not be immediately life-threatening or result in death or hospitalization, but based on medical judgment may jeopardize the subject and may require medical or surgical intervention to prevent any of the outcomes listed above (i.e., death of subject, life-threatening, hospitalization, prolongation of hospitalization, congenital anomaly, or persistent or significant disability/incapacity). Examples of such events include allergic bronchospasm requiring intensive treatment in an emergency room or at home, blood dyscrasias or convulsions that do not result in inpatient hospitalization, or the development of drug dependency or drug abuse as well as spontaneous or elective abortions, stillbirths and ectopic pregnancies)

6.12.1.8. Reporting Serious Adverse Events

Any SAE (fatal or life-threatening SAE and other SAEs), whether or not related to the study drug, must be reported immediately within 24 hours of the investigator's awareness of the event by telephone, faxing and email the appropriate SAE forms to the following numbers:

Study Medical Monitor

After office hours, the emergency telephone number is:

If a subject should become pregnant during the study, the event will be reported within 1 day of the investigator's knowledge of the pregnancy.

If pregnancy occurs in a subject from the time of ICF signature who does not qualify for allocation to treatment, i.e. Screen Failure, the pregnancy should be recorded in patient's medical file only, in accordance to local requirements. The pregnancy related medical status change information will not be reviewed by Abbott or delegated staff. The pregnancy will not qualify as a study (S)AE.

If pregnancy occurs in a subject from the time of ICF signature who is not disqualified for allocation to treatment, the pregnancy should be recorded in patient's medical file in accordance to local requirements and in Abbott's pregnancy from. The pregnancy related medical status

Confidential Page 62 of 94

change information will be reviewed by Abbott or delegated staff. The pregnancy will not qualify as a study (S)AE.

The pregnancy evolution and outcome, i.e., the health status of the newborn, is to be reported on the Pregnancy Outcome Form

Pregnancy in a study subject is not considered an adverse event. However, the medical outcome of an elective or spontaneous abortion, stillbirth, ectopic pregnancy or congenital anomaly is considered a SAE and must be reported to within 24 hours of the investigator becoming aware of the event and followed-up as described in Section 6.12.2

6.13. Emergency Situation Procedures

The Investigator is responsible for obtaining information on all the patient's emergency medical conditions in the course of the study. The text of the Patient Information Sheet and Informed Consent Form should contain the Investigator's contact information. The patients will be recommended to contact the Investigator in the event of any emergency conditions occurring during the study.

6.14. Subject Withdrawal from the Study

All subjects are free to withdraw from participation in this study at any time, for any reason, specified or unspecified, and without penalty or loss of benefits to which the subject is otherwise entitled.

The Study Termination form must be completed for all subjects who did not fail screening.

In case of premature termination of the subject from the study, the primary reason for this premature termination is to be indicated according to the following definitions:

- Adverse event: discontinuation due to any adverse event (AE) with a corresponding entry reflected on the Adverse Events form in the eCRF
- Lack of efficacy: subject fails to respond to the study drug at an acceptable level where the subject or the Investigator feels it is in the best interests of the subject to seek another treatment.
- Lost to follow-up: the subject fails to return to the study site for scheduled visits and does not respond to telephone or written attempts to contact.
- Withdrew consent: subject decides to stop his/her participation in the study for any reason other than an AE, or is unable to complete the study as described in the clinical study protocol (e.g., subject is relocating to another location).
- Administrative: the Sponsor decides to discontinue the study (either at the study site or the entire study), e.g., general safety problems leading the Sponsor to entirely stop the study.
- Protocol violation anything which is in direct violation of the clinical study protocol (e.g., inclusion/exclusion violation)

If possible, the Investigator must first discuss the discontinuation with the Medical Monitor. Otherwise, the Investigator should discuss the issue of discontinuation with the Medical Monitor within 24 hours after discontinuation.

The reason for the patient's discontinuation should be specified in the source documentation and on the electronic Case Report Form. If the patient discontinues participating in the study for more than one reason, the main reason should be given. Occurrence of an AE or SAE should be specified as the reason for the withdrawal of the patient's consent due to such AE or SAE.

Confidential Page 63 of 94

In addition, the Sponsor shall be entitled to terminate the study at any time. The Investigator is entitled to terminate the study at any time for medical or regulatory reasons. Termination of the study should be done after mutual consultations between the Investigator and the Sponsor only.

If the study is terminated ahead of time, all patients should undergo early termination visit procedures, and all study documents must be returned to the Sponsor or its representative.

Follow-up of AE, SAE and pregnancy continuing at the time of the study termination should be performed as per the Protocol, unless another procedure for the safety follow-up is agreed between the Investigator and the Sponsor.

6.15. The validity of measurements

Evaluations of the efficacy and safety of therapy in patients with functional diseases of the colon are standard and well known. A randomized, controlled, parallel-group clinical study will evaluate the safety and efficacy of the study drug versus reference drugs.

Due to the COVID-19 pandemic, visits to the study site can be replaced by home visits by the site's employees or the use of telemedicine opportunities. These changes, including the permissible amount of missing data, should be approved by the Sponsor and IEC and do not require amendments to the protocol (in case it is ongoing at the moment of the study treatment phase).

7. STUDY PROCEDURES

7.1. Screening and run-in period (Visit 1, Week – 1, Day -7)

Visit window day -21....-7

- The procedure for obtaining the informed consent
- Patient Registration
- Collection of demographic data, medical history and concomitant medication data
- Physical examination
- Assessment of vital signs
- Measuring height, weight, BMI
- Abdominal pain intensity on the NRS-11 scale evaluation (worst pain for the latest 3 months)
- Bloating/Flatulence intensity on the NRS-11 scale evaluation (worst bloating episode for the latest 3 months)
- ECG
- Blood sampling for safety laboratory tests (hematology and blood chemistry, tests for HIV, hepatitis B and C)
- Urine collection for urinalysis
- Feces sampling for Fecal calprotectin analysis (if there is no result in 1 month before screening)
- The urine pregnancy test is carried out on women with child-bearing potential (including women in the menopausal period of less than two years)

Confidential Page 64 of 94

¹ Week -3, Day -21 in case of colonoscopy

- Assessment of inclusion/non-inclusion criteria
- Patient diary dispense
- Colonoscopy should be performed in patients over 50 years of age who do not have a colonoscopy report on the absence of significant colon pathology in the last 12 months who meet all inclusion/exclusion criteria (excluding Inclusion Criteria 5 and 6 that are to be evaluated at a randomization visit). Colonoscopy should be performed not later than 10 days before the randomization visit.

Patient questionnaires, tests, and scales should be completed according to the adopted clinical practice by the certified trained member of the Site study team before dosing.

In case of ambiguous or controversial results of laboratory tests, a single repeated test (retest) may be performed, as agreed with the Sponsor or its representative.

Patients that do not meet all inclusion/exclusion criteria will not be included in the study. Patients not enrolled in the study due to conditions which may be corrected may be re-screened one time, as agreed upon with the Sponsor or its representative.

From this date intake of drugs prohibited by the protocol are not allowed. Intake of drotaverin in a dose of 80 mg 1-3 times a day will be allowed to stop intensive pain episode during one day after the episode.

7.2. Treatment period

7.2.1. Randomization (Visit 2 Week 0, Day 1).

- Assessment of AE and concomitant medication
- Measuring, weight, BMI
- Assessment of vital signs
- Abdominal pain and bloating/flatulence intensity on the NRS-11 scale evaluation
- Patient diary assessment (Including stool consistency in line with the Bristol stool scale, stool frequency, drotaverine intake and menstrual bleeding days)
- Assessment of inclusion/non-inclusion criteria
- Randomization
- Evaluate the quality of life (IBSQOL questionnaire)
- Study drug dispense

7.2.2. Telephone contact 1 (Week 2, Day 15)

Visit window ± 1 day

 Assessment of AE and concomitant medication, study drug intake, interrogation for correctness of patient diary filling

7.2.3. End of treatment (Visit 3, Week 4, Day 29)

Visit window ± 1 day

- Assessment of AE and concomitant medication
- Measuring, weight, BMI
- Physical examination

Confidential Page 65 of 94

- Assessment of vital signs
- Blood sampling for safety laboratory tests (hematology and blood chemistry)
- Urine collection for urinalysis
- Patient diary assessment (daily data for 4 weeks, including abdominal pain and bloating/flatulence intensity, stool consistency in line with the Bristol stool scale, stool frequency, drotaverine intake and menstrual bleeding days)
- Evaluate the quality of life (IBSQOL questionnaire)
- Study drug return, accountability and compliance assessment

At this point the period of the study therapy is completed. The patient will be given recommendations for further treatment as part of standard therapy

7.3. Follow-up period

7.3.1. Telephone contact 2 (Week 5, Day 36)

Visit window +1 day

• Assessment of AE and concomitant medication

7.4. Unscheduled visits

At the discretion of the Investigator, the patients may be invited for an unscheduled visit at any time in the course of the clinical study for safety reasons, in case a re-examination or repeated procedure is required, or to provide additional quantity of the study drug. During unscheduled visits, the Investigator may conduct the necessary procedures. Unscheduled visits should be registered in the source documentation and CRF. Unscheduled visits should not affect the schedule of planned visits provided by the Protocol of this clinical study

7.5. Early discontinuation visit

In case of early termination of participation, after Visit 2 (Week 0, Day 1) and before Visit 3 (Week 4, Day 29), the patient should be invited to the study site to undergo an early discontinuation Visit (ED) assessments. The Investigator should make every effort to conduct ED

ED Visit should include all procedures of Visit 3 (Week 4, Day 29). If ED Visit cannot be carried out in full, the Investigator should coordinate their actions with the Medical Monitor. On ED Visit the patient should return all used and unused packages of the study drug. The patient will be given recommendations for further treatment as part of standard therapy.

If possible, the Investigator should discuss the patient's early discontinuation from the study with the Medical Monitor in advance. Otherwise, the Investigator should contact the Medical Monitor within 24 hours after the early discontinuation of the patient

8. QUALITY ASSURANCE

This clinical study will be conducted in accordance with Standard Operating Procedures (SOP) of the Sponsor and/or representatives thereof, the requirements of International Conference on Harmonization Good Clinical Practice Guidelines (ICH GCP(E6)) and Eurasian Economic Union (EEU), principles provided in Helsinki Declaration, as well as in accordance with the applicable legislation and regulations of the Russian Federation. Compliance with the requirements will be provided by audits of the study site and the data obtained in the study.

The Investigator will enter the data required in accordance with this Protocol into the eCRF, provided by the Sponsor or the representative thereof. The monitors shall visit each study site at a frequency described in the monitoring plan to check the eCRFs for completeness and accuracy of

Confidential Page 66 of 94

filling. Specifying question shall be asked concerning any differences between the source documentation and completed eCRFs, which the Investigator should answer and/or eliminate these inconsistencies. When all the information required had been entered and all the specifying questions clarified, the Investigator should sign and date the eCRF of each patient. The completed pages of the eCRF will be checked during the monitoring visits..

Due to the COVID-19 pandemic, a centralized and remote monitoring model can be used in the study. All applicable principles will be described in the monitoring plan.

9. STATISTICAL METHODS PLANNED

9.1. General provisions

This is clinical study to evaluate efficacy and safety of Mebeverine+Simethicone fixed-dose combination versus Duspatalin® (mebeverine) and versus Espumisan® (simethicone) in patients with functional bowel disorders with abdominal pain and excess gas formation.

Statistical analysis, described in the following subsections, will be performed as specified in the Statistical analysis plan, which will be created and finalized before closing the database. The Statistical analysis plan will be included in the report on the clinical study for this Protocol.

9.2. Sampling size identification

In first amendment to protocol the pre-specified interim analysis was removed. However, as already all subjects were recruited no change in sample size was made. Note that a design without the interim analysis needs less patients to achieve the same power, so that deleting the interim did not have negative consequences to the power of the study while maintaining still the usual type 1 error rate of 5% (two-sided). For sake of completeness below the original sample size rationale is given.

There are no published data on bloating/flatulence and abdominal pain assessment with NRS-11 for simethicone versus placebo and mebeverin versus placebo. Comparison of Linaclotide treatment versus placebo for bloating decrease in chronic constipation patients was assessed with NRS-11 and found out 1.0 point difference between groups with approximately 2.5 standard deviation. Comparison of B. coagulans Unique IS2 treatment versus placebo for pain decrease in IBS patients was assessed with NRS-11 and found out 3.2 point difference between groups with 2.5 standard deviation.

An assumption was taken that Mebeverin+Simethicone fixed dose combination will decrease the sum of pain and bloating/flatulence scores on average at least 1.0 point more than simethicone or mebeverine as monotherapy.

For primary endpoint to demonstrate the superiority of the FDC versus separately each monocomponent assuming an expected 1.0 point difference between the two treatment groups and standard deviation 2.5 with type I error $\alpha = 0.05$ (two-sided) and a power 90% for each comparison individually in a group-sequential design with one interim stage at information fraction 40%, about 132patients should be included in both groups. The overall power to demonstrate superiority for both comparisons (FDC vs mebeverine monotherapy and FDC vs simethicone monotherapy) is about 80%.

Thus, 396 should be included into the analysis

3.	mebeverin	superiority/sum NRS-	$\alpha = 0.05$ (two-sided)	n1 = n2 = 132
		11 scores for pain and	$\beta = 0.1$	
		bloating/flatulene	Power = 90%	
		intensity	Mean diff. $= 1.0$	
		-	SD = 2.5	
			Alpha spending function:	
			O'Brien-Fleming	

Confidential Page 67 of 94

		Beta spending function (non-binding): O'Brien-Fleming Max. num, of stages = 2 Info. proportion at Interim stage = 0.40	
4. simethicone	superiority /sum NRS- 11 scores for pain and bloating/flatulene intensity	α = 0.05 (two-sided) β = 0.1 Power = 90% Mean diff. = 1.0 SD = 2.5 Alpha spending function: O'Brien-Fleming Beta spending function (non-binding): O'Brien-Fleming Max. num, of stages = 2 Info. proportion at Interim stage = 0.40	n1 = n2 = 132

Thus, taking into account a 15% drop-out rate, about 155 patients should be included in each group. A total of 465 patients should be randomized..

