For primary endpoint to demonstrate the superiority of the FDC versus separately each mono-component assuming an expected 1.0 point difference between the two treatment groups and standard deviation 2.5 with type I error $\alpha = 0.05$ (two-sided) and power 90% for each comparison individually in a group-sequential design with one interim stage at information fraction 40%, about 132 patients should be included in both groups. The overall power to demonstrate superiority for both comparisons (FDC vs mebeverine monotherapy and FDC vs simethicone monotherapy) is about 80%.

Thus, 396 should be included into the analysis.

1. mebeverin	superiority /sum	$\alpha = 0.05$ (two-sided)	n1 = n2 = 132
	NRS-11 scores for	$\beta = 0.1$	
	pain and	Power = 90%	
	bloating/flatulene	Mean diff. $= 1.0$	
	intensity	SD = 2.5	
		Alpha spending function:	
		O'Brien-Fleming	
		Beta spending function (non-binding):	
		O'Brien-Fleming	
		Max. num, of stages $= 2$	
		Info. proportion at Interim stage = 0.40	
2. simethicone	superiority /sum	$\alpha = 0.05$ (two-sided)	n1 = n2 = 132
	NRS-11 scores for	$\beta = 0.1$	
	pain and	Power = 90%	
	bloating/flatulene	Mean diff. $= 1.0$	
	intensity	SD = 2.5	
		Alpha spending function: O'Brien-Fleming	

Confidential Page 14 of 94

O'Brie Max. n	pending function (non-binding): n-Fleming num, of stages = 2 roportion at Interim stage = 0.40
------------------	--

Thus, taking into account a 15% drop-out rate, about 155 patients should be included in each group. A total of 465 patients should be randomized.

Randomization

Patients will be randomized into three equal groups (1:1:1) using the IWRS system.

Protocol version number and date:

Protocol MESI3001 Amendment 1 dated 07 April 2021

Confidential Page 15 of 94

TABLE OF CONTENTS

PROTOCOL APPROVAL PAGE2	
PRINCIPAL INVESTIGATOR STATEMENT	
CONTACT INFORMATION ON CLINICAL STUDY4	
SYNOPSIS6	
TABLE OF CONTENTS	
LIST OF TABLES	
LIST OF FIGURES20	
LIST OF ABBREVIATIONS21	
1. INTRODUCTION 22	

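### The SD of 2.5 used to power the sum of two NRS-11 scores is cited only for single scores, so the stated 90% / about 80% power is unsupported and probably too high

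*Protocol*

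**What the plan says.** Protocol section 9.7.1 defines the primary endpoint as the Week 4 change in the sum of two NRS-11 scores, each 0 to 10, so the sum runs from 0 to 20. Section 9.2 places the assumed effect on that same sum: the combination is expected to "decrease the sum of pain and bloating/flatulence scores on average at least 1.0 point more than simethicone or mebeverine as monotherapy". The calculation is then run "assuming an expected 1.0 point difference between the two treatment groups and standard deviation 2.5 with type I error" 0.05 two-sided. Both rows of the sample-size table carry SD = 2.5 and are labelled as the sum.

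Two published studies are given as the source of the SD. A bloating study in chronic constipation "found out 1.0 point difference between groups with approximately 2.5 standard deviation". A pain study in IBS "found out 3.2 point difference between groups with 2.5 standard deviation". Each used a single NRS-11 score.

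From these inputs the synopsis concludes that "about 132 patients should be included in both groups" and section 9.2 gives 396 evaluable patients in total, raised to 155 per arm for 15% drop-out. Power is stated as 90% for each comparison, and "The overall power to demonstrate superiority for both comparisons (FDC vs mebeverine monotherapy and FDC vs simethicone monotherapy) is about 80" percent. Amendment 1 removed the interim analysis and adds that "deleting the interim did not have negative consequences to the power of the study". Under section 9.7.2 the study succeeds only if both comparisons do.

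**The concern.** The effect and the endpoint are on the sum, but the SD comes from its components. A sum of two positively correlated scores varies more than either score alone, so a component SD cannot simply be carried over. Sections 3.5.1 and 3.5.3 justify adding the scores on the ground that the symptoms are related. That argues against the negative correlation needed to keep the SD of the sum at 2.5. Section 9.2 gives no SD for the sum, no correlation between the two scores, and no allowance for variance removed by baseline adjustment.

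At stake is the only power statement for a rule that requires two wins. A reader who takes 90% / about 80% at face value would think the trial better powered than its own cited inputs show, and could read too much into a comparison that fails.

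**Working it through.** **Inputs from protocol 9.2.** Difference δ = 1.0 on the sum; SD 2.5; two-sided α = 0.05; 132 evaluable and 155 randomised per arm; both comparisons must succeed.

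**Assumptions not in the documents.** ρ is the correlation between the two component scores (0, 0.5, 1). r is the correlation between baseline and change in the sum (0 or 0.5). Site effects are ignored. The documents also do not say whether the cited SDs are for raw scores or for change; they are treated here as SDs of change.

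**Step 1: reproduce the plan's figure.** Fixed-design n = 2 × (1.960 + 1.2816)² × 2.5² / 1.0² = 131.3, so 132 per arm. Restoring the original interim look at 40% information gives 131.5 per arm without futility stopping, or 132.8 if the futility boundary is acted on. Power at 132 per arm, by noncentral t with 2n − 2 degrees of freedom, is 89.9%. For both comparisons, a bivariate normal with correlation 0.5 (the shared combination arm) gives 83.5%; multiplying two independent 90% powers gives 81%. For drop-out, 132 / 0.85 = 155.3. The plan's arithmetic therefore follows from its inputs. The problem is the SD.

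**Step 2: SD of the sum.** With component SD c, SD(sum) = c × √(2(1+ρ)). For c = 2.5:

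- ρ = 0: 2.5 × √2 = 3.54
- ρ = 0.5: 2.5 × √3 = 4.33
- ρ = 1: 2.5 × 2 = 5.00
- SD(sum) = 2.5 requires 2(1+ρ) = 1, so ρ = −0.5

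Conversely, a sum with SD 2.5 needs component SDs of 1.77 (ρ = 0), 1.44 (ρ = 0.5) or 1.25 (ρ = 1).

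**Step 3: power.** Residual SD = SD(sum) × √(1 − r²), and the noncentrality is δ / (residual SD × √(2/n)). For example, with n = 132, ρ = 0 and r = 0 it is 1 / (3.536 × 0.1231) = 2.30, giving 62.9% per comparison. Entries are power per comparison / for both, in percent.

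| Component SD | r | ρ | 132 per arm | 155 per arm |
|---|---|---|---|---|
| 2.5 (cited) | 0 | 0 | 62.9 / 47.6 | 69.9 / 55.9 |
| 2.5 | 0 | 0.5 | 46.4 / 30.1 | 52.7 / 36.3 |
| 2.5 | 0 | 1 | 36.7 / 21.2 | 41.9 / 25.8 |
| 2.5 | 0.5 | 0 | 75.3 / 62.8 | 81.8 / 71.5 |
| 2.5 | 0.5 | 0.5 | 57.9 / 41.9 | 64.8 / 49.7 |
| 2.5 | 0.5 | 1 | 46.4 / 30.1 | 52.7 / 36.3 |
| 2.0 (assumed) | 0 | 0 | 81.6 / 71.4 | 87.3 / 79.5 |
| 2.0 | 0 | 0.5 | 64.7 / 49.6 | 71.7 / 58.1 |
| 2.0 | 0.5 | 0 | 91.1 / 85.2 | 94.8 / 91.0 |
| 2.0 | 0.5 | 0.5 | 77.0 / 65.0 | 83.3 / 73.6 |

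A three-arm simulation at 132 per arm with component SD 2.5 agrees: 63.0 / 47.4 (ρ = 0, r = 0), 46.5 / 29.9 (ρ = 0.5, r = 0) and 75.4 / 62.6 (ρ = 0, r = 0.5).

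**Step 4: what would rescue the claim.** Joint power of 80% needs a residual SD of at most 2.60 at 132 per arm, or 2.81 at 155. With component SD 2.5 that means r of at least √(1 − (2.60/3.54)²) = 0.68 at ρ = 0, or 0.80 at ρ = 0.5. At 155 per arm it means 0.61 or 0.76.

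**Step 5: detectable difference.** Unadjusted, 90% power at 132 per arm corresponds to (1.960 + 1.2816) × SD(sum) × √(2/132), which is 1.41 points at ρ = 0 and 1.73 at ρ = 0.5.

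**Step 6: if 1.0 per scale was meant.** A difference of 2.0 on the sum with component SD 2.5 gives 89.9% / 83.5% at 132 per arm even at ρ = 1, and more at smaller ρ.

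**The case against.** The strongest reply is that the plan's arithmetic is correct and the size of any loss is unknown. It depends on ρ, on r and on this trial's component SD, none of which the documents give. The cited SDs come from other drugs against placebo in other populations. This trial averages seven daily scores and selects patients with 4 to 9 points on both scales, so even a single score's SD could differ from 2.5. The full analysis set is broad, so the number analysed could approach 155 per arm. There, an assumed component SD of 2.0 with ρ = 0 gives 87% / 79.5% with no adjustment, close to the stated joint power. Finally, recruitment is over and section 9.2 says the rationale is kept only for completeness.

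Much of this stands as a limit on precision. The loss can only be given as a range, and favourable combinations exist. It does not supply the missing basis: each rescue needs a component SD, a correlation or a variance reduction that the plan does not state. With SD 2.0 at 155 per arm, ρ = 0.5 and r = 0.5, joint power is still only 74%. The historical label does not settle the matter either. The synopsis repeats the power claim without that label, and Amendment 1 adds a fresh statement about power.

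**Conclusion.** The concern holds. The stated power rests on an SD for the sum that the protocol cites only for its components. With the cited component SD and any non-negative ρ, neither 90% per comparison nor 80% for both is reached without strong baseline adjustment, which section 9.2 does not mention. Unadjusted joint power is then about 21% to 48% at 132 per arm and 26% to 56% at 155. With an assumed baseline–change correlation of 0.5 it is 30% to 63% and 36% to 71.5%.

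That no basis is given for the SD is certain. That power is overstated is probable, and its extent depends on the assumed correlations and component SD. The statement about removing the interim look is right as a relative comparison, but it does not show that 90% / about 80% is achieved. Endpoint, model, type I error and success rule are untouched. This should be fixed because the figure will be relied on.

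**What to change.** Keep the original rationale in section 9.2 and the synopsis, but correct or annotate the power claim:

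1. State that SD 2.5 was cited for single scores and that the SD of the sum is 2.5 × √(2(1+ρ)).
2. Tabulate individual and joint power at 132 and 155 per arm for ρ = 0, 0.5 and 1, without baseline adjustment and with a stated baseline–change correlation, all labelled as assumptions.
3. Give the unadjusted difference detectable with 90% power at 132 per arm: about 1.41 (ρ = 0) and 1.73 (ρ = 0.5).
4. Check the planning records. If they show that 1.0 per scale (2.0 on the sum) was intended, correct the assumed difference instead. Do not adopt 2.0 now without such a record.
5. Keep the sentence on the interim analysis, and add that it does not establish the stated power.

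The cost is one note and one small table in two places. No patients, data or analyses change. The drawback for the sponsor is a less favourable stated power.
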